## 23.0 Withdrawal of Research Participants

**Under what circumstance(s) would you withdraw a research participant from the research without their consent? (Check all that apply)**

- Safety Reasons; please explain [Click here to enter text.](#)
- Not following study instructions
- Being suspected of being a bot or bad actor (online surveys only)
- Other; please explain If a participant's eligibility criteria changes, in that they are no longer able to attend in-person classes or in-person assessments.
- N/A; please explain [Click here to enter text.](#)
- None

**Describe any procedures when a research participant withdraws or are withdrawn from the research, including partial withdrawal from procedures with continued data collection.**

If a participant withdraws or is withdrawn from the study, their associated data and identifiers will be removed from the dataset and destroyed within 30 days of the participant providing notice to the research team. If a participant withdraws but has already submitted some class assessment surveys, these will remain as part of the dataset due to the anonymous nature. Pre-assessment data will not be retained.

- N/A

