## 4.0 Inclusion and Exclusion Criteria

### Directions: Describe how individuals will be screened for eligibility.

Individuals will be verbally screened for eligibility to determine they are 18 years of age or older and determine that they are able to attend in-person, Nourish classes.

**Using the tables below, describe the inclusion and exclusion criteria that will define who will be included and excluded in your final study sample.**

Inclusion	
1.	Age range: Adults aged 18 and over
2.	Ability to attend classes (in person)
3.	
4.	

Exclusion	
1.	Non-English speaking
2.	
3.	
4.	

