## 9.0 Setting

**Directions: Describe the sites and locations where your research team will conduct the research.**

Baseline assessment meeting: Participants will meet the Nourish research team at a reserved room located at a branch of the Cleveland Public Library. Weekly Nourish classes: For the duration of 8 weeks, the Nourish culinary education intervention will take place at a community teaching kitchen located at Dave's Market Midtown ([name]) or CornUcopia ([name]). Second-assessment meeting: Participants will meet the Nourish research team at a reserved room located at a branch of the Cleveland Public Library. Focus Group Series: Participants who complete at least 7 of the 8 Nourish classes will be invited to participate in 2, 90-minute semi-structured focus groups. These will take place online via Zoom.

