## 12.0 Study Design/Procedures

### Directions:

- 1) **Describe the overall study design (e.g.: single visit, single-blind, double-blind, non-randomized, randomized, blood draw, investigational drug, device etc.).**
- 2) **Provide a description of all study-related research procedures being performed, including the length of time involved.**
- 3) **Include procedures being performed to monitor research participants for safety or minimize risks.**
- 4) **Describe the source records including medical or educational records, which will be used to collect data about subjects.**
- 5) **Include a description of any device being used to collect data (e.g., eye tracker, step counter). If the device itself is being studied, include additional information in Section 29.**

1. The study follows a randomized controlled trial with a delayed intervention control design. The immediate cooking class group will receive their intervention in week 3 of the study, and the delayed cooking class group will receive their intervention in week 13 of the study.

2. *Baseline assessment meeting:* Regardless of randomized group, all participants will attend this meeting in week 1. Participants will come to a branch of the Cleveland Public Library to sign their consent form and complete the survey portion of their baseline assessment, consisting of Percieved Stress Scale, USDA Food Security Screener, and the Food Literacy, Environment, and Waste (FLEW) assessment which will be conducted via Qualtrics on tablets provided by the researchers. Two aspects of the baseline evaluation will be conducted after the baseline meeting: a) a series of two 24-hour dietary recalls (via phone calls) lasting approximately 30 minutes each and b) participants will be asked to weigh and log their food waste for one week. During the baseline assessment meeting, participants will be asked to share their phone number and participants will be given a kitchen food scale and waste log. They will be asked to return the log on the first day of class. Additionally, participants will be told what they can expect to happen at each Nourish class and will be coached on how to sign up for GroupMe to receive out-of-class information about Nourish. The duration of the baseline assessment meeting will be

approximately 60 minutes, and will occur two weeks before the immediate cooking classes group's 8-week Nourish class sessions begin.

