*Weekly Nourish classes:* Each Nourish class will last 90 minutes, and will run for 8 consecutive weeks, with one class per week. The immediate cooking class group will receive the Nourish classes in weeks 3-10, and the delayed intervention group will commence the Nourish intervention in weeks 13-20 (after the second intervention assessment period is complete).

Nourish will be held in the teaching kitchen at Dave's Market or CornUcopia. Each class will involve brief instructional video clips, hands-on cooking and tasting experiences. Participants will work individually and as part of small groups during instructional sessions. At the end of each class, participants will receive a grocery bundle and a kitchen gadget that serves both as an incentive and implementation support to promote improved cooking frequency and confidence. Participants will be asked to post photos of what they made with their groceries to the GroupMe, and we will encourage them to engage with fellow classmates on the GroupMe to encourage social support of cooking. Participants will earn raffle tickets for each time they post to the GroupMe and attend a class. A raffle drawing for a pressure cooker will be done at the second-assessment meeting (week 12) for the immediate cooking class group and at the last Nourish class for the delayed group (week 20).

The delayed intervention group will commence the Nourish intervention after the post-intervention assessment period is complete (in weeks 13-20).

A research assistant will attend each class to observe time use and lesson objectives covered.

*Second assessment meeting:* Participants will come to a branch of the Cleveland Public Library to complete their post assessment, consisting of PSS, USDA Food Security Screener, and the FLEW, as well as their return food waste log. Additionally, participants will be encouraged to enroll in an optional focus group series to provide feedback on Nourish. The duration of the second-assessment meeting will be approximately 35 minutes, and will occur in Week 12.

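### Section 23 treats inability to attend classes as leaving the research and destroys the person's data, baseline included; before week 12 this falls more heavily on the immediate arm

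*Combined protocol and SAP*

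**What the plan says.** Section 23.0 (Withdrawal of Research Participants) gives, as a reason for withdrawing someone without consent, a change in eligibility such that "they are no longer able to attend in-person classes or in-person assessments". The consequence is the same for voluntary and imposed withdrawal: "If a participant withdraws or is withdrawn from the study, their associated data and identifiers will be removed from the dataset and destroyed". The deadline for this is 30 days after notice. It adds: "Pre-assessment data will not be retained". The one exception is class surveys already submitted, which stay because they are anonymous; none of them is an ANCOVA outcome. The form asks for procedures "including partial withdrawal from procedures with continued data collection", and the answer provides none.

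Section 12.0 places the immediate arm's classes in weeks 3-10 and the delayed arm's in weeks 13-20. Of the follow-up shared by both arms it says: "The duration of the second-assessment meeting will be approximately 35 minutes, and will occur in Week 12". Section 9.0 gives its location: "Second-assessment meeting: Participants will meet the Nourish research team at a reserved room located at a branch of the Cleveland Public Library". Classes are 90 minutes each, at a teaching kitchen. Baseline diet is measured by "a series of two 24-hour dietary recalls (via phone calls) lasting approximately 30 minutes each"; Section 15.0 lists four recalls per participant, and the mode of the later two is not restated.

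Section 17.0 measures retention by the number who complete the post-intervention assessments. It then plans, as an additional analysis, an ANCOVA of each outcome adjusted for its baseline value. It names no analysis population and no handling of missing data.

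**The concern.** Two different events are merged: no longer being able to come to classes, and leaving the research. The first need not end data collection, because the week-12 visit is one short meeting at a different place. The rule can therefore remove people who would still have supplied a week-12 score, together with the baseline score they had already given.

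Before week 12 the removal is uneven by design. The immediate arm has eight class weeks in which inability to attend can arise; the delayed arm has none. If those removed differ in outcome from those who stay, the two arms are no longer comparable as randomised.

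The rule also has no end date. A delayed-arm participant who leaves in weeks 13-20 has already given valid week-1 and week-12 control data. If the analysis is run after week 20 (its timing is not stated), those data are gone.

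For Aim 2, which covers retention, the count survives. What is lost is any description of leavers' food security, stress and diet at baseline, the information a planned larger study would want. Destroyed data cannot be recovered.

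**Working it through.** **No figure to reproduce.** The documents state no power, effect size, SD or dropout rate. The check therefore sets the rule against the schedule and then illustrates size under stated assumptions.

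**Step 1: exposure to the trigger, from the start of classes to week 12 (Section 12.0).**

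- Immediate arm: 8 classes + 1 assessment = 9 in-person obligations.
- Delayed arm: 0 classes + 1 assessment = 1.

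The assessment trigger applies to both arms. The class trigger is lower, not zero, in the delayed arm: being able to attend classes is an entry criterion for everyone (Section 4.0), and someone could report early that later classes will be impossible.

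**Step 2: bias in the planned ANCOVA.**

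- From the documents: 20 per arm (Section 5.0); outcome adjusted for baseline (Section 17.0).
- Assumed: no true effect; baseline-outcome correlation 0.5; a tendency to leave that correlates 0.3 or 0.5 with outcome and either zero or equally with baseline.
- Under the rule, those with the highest tendency to leave are removed. After the fix, a random half of them return with week-12 data.
- 40,000 simulated trials per scenario; Monte Carlo standard error of the bias about 0.0015 SD. Signs are dropped because the direction is unknown.

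Each cell shows bias in SD / rejection rate at a nominal 5%:

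| Removed (immediate, delayed) | Correlation with outcome, baseline | Under the rule | After the fix | Due to the rule (SD) |
|---|---|---|---|---|
| 25%, 10% | 0.3, 0.3 | 0.032 / 5.2% | 0.011 / 4.9% | 0.021 |
| 25%, 10% | 0.3, 0 | 0.069 / 5.8% | 0.029 / 5.2% | 0.040 |
| 25%, 10% | 0.5, 0.5 | 0.061 / 5.7% | 0.024 / 5.1% | 0.038 |
| 25%, 10% | 0.5, 0 | 0.111 / 7.6% | 0.044 / 5.6% | 0.068 |
| 25%, 0% (limiting case) | 0.3, 0.3 | 0.063 / 5.6% | 0.028 / 5.3% | 0.035 |
| 25%, 0% (limiting case) | 0.5, 0 | 0.203 / 10.9% | 0.088 / 6.1% | 0.116 |

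The last column is the difference of the two before it, taken before rounding. The two limiting-case rows are the smallest and largest of four. With 25% removed from both arms the bias is about 0 and rejection 5-6%.

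Sensitivity to the share who would still attend week 12, for 25% and 10% removed: the part due to the rule is 0.012-0.038 SD if a quarter would attend and 0.028-0.092 SD if three quarters would.

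Only the last column belongs to Section 23. People who would give no week-12 score are lost with or without it.

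**Step 3: late destruction of delayed-arm records.** Standard error = sqrt(1 − 0.5²) × sqrt(1/20 + 1/n₂), in SD units.

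- n₂ = 20: 0.866 × 0.316 = 0.274; × t(37) = 2.026 gives a 95% half-width of 0.555.
- n₂ = 15 (5 of 20 records destroyed): 0.866 × 0.342 = 0.296; × t(32) = 2.037 gives 0.603.

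**Step 4: what leavers' baseline data could show.** For 5 leavers against 35 stayers, the half-width is t(38) × sqrt(1/5 + 1/35) = 2.024 × 0.478 = 0.968 SD. That supports description, not a test.

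**The case against.** The strongest reply is that the trigger is narrow. It needs a person to become unable to attend; missing classes is not enough. The protocol plainly tolerates absence: focus groups are limited to those completing at least 7 of 8 classes, and bundles and survey payments follow each class attended. Someone who simply stops coming is not withdrawn by this text. That is right, and it limits how many people the rule reaches. It does not change what happens to those it does reach.

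Second, harm from the rule needs a person who becomes unable to attend, is formally withdrawn, and could and would still complete week 12. The documents give no rate for any of these, and the number could be near zero. This stands, which is why the figures are only an illustration.

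Third, even on those figures the effect is small: 0.02-0.07 SD against a half-width of 0.55 SD, in an analysis that is additional to three feasibility aims and carries no power claim. This also stands. But Section 17.0 does plan significance tests between the arms, and retention is itself an aim.

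Fourth, deletion by default may be a deliberate protection, and the consent form was not available for this review. That is a genuine trade-off. Deletion on request, and honouring terms already given, keeps most of the protection. It also matters that, under the imposed route, data are destroyed although the person never asked for that.

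Finally, a stated analysis population would be needed in Section 17.0 whatever Section 23.0 says. That is so, but without it the data kept by the fix might still be left out of the comparison.

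**Conclusion.** The concern holds and should be fixed. On the text, Section 23.0 makes inability to attend classes a withdrawal from the research and destroys the data, baseline included. On the schedule, exposure to that trigger before week 12 is greater in the immediate arm.

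The size is uncertain and probably modest. With 25% and 10% removed and half of those still able to give week-12 data, the rule accounts for 0.02-0.07 SD of false difference, and type I error is 5-8% under the rule against 5-6% after the fix. In the limiting case, with removals from the immediate arm only, it accounts for 0.04-0.12 SD, with 6-11% under the rule. With equal removal there is no bias. All removal rates, correlations and return shares are assumptions, and the direction of any bias is unknown.

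The loss of delayed-arm records in weeks 13-20 depends on unstated analysis timing and costs precision: five records would widen the half-width from 0.55 to 0.60 SD. Confidence is medium. The box marks did not survive in the text, and the trigger is read as active because the study team filled in its wording. The case for acting rests on irreversible loss set against a cheap remedy, not on a large expected bias.

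**What to change.** In Section 23.0, and in the consent form where it states the deletion rule:

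1. Keep coded data collected before withdrawal, baseline included, unless the participant asks for deletion. Honour any deletion terms already given to people who have consented.
2. Treat inability to attend classes as stopping classes, not as withdrawal from the research, and still invite the person to the week-12 assessment.

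In Section 17.0:

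3. Analyse everyone with week-12 data in the group to which they were randomised.
4. Report withdrawals by arm, timing and reason, with baseline values, as description only.

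The cost is one protocol amendment and, if needed, matching wording for new consents. There are no new visits or procedures. The downside is that leavers' coded data are kept by default, which gives up a default that may have been meant to protect participants; deletion on request is the safeguard. The change does not remove bias from people who give no week-12 score.

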## 24.0 Alternatives to Participation

**Directions: List other options to participation. If subjects will be compensated with extra course credit, the course instructor offering extra course credit must provide alternatives to earn extra course credit. The alternative assignment must require equal or less time and effort for the same amount of earned extra credit that you can earn through participation in research. If there are other available clinical treatments, what would be included if a subject continued on standard of care therapy. If there is a viable alternative you must list it in the consent.**

[Click here to enter text.](#)

- The alternative is for research subjects not to participate.

## 25.0 Costs to Research Participants

- There are no costs to research participants or their insurance companies (there are no clinical visits or billable procedures.) *– please leave rest of this section blank*

1. Describe what costs research participants will be responsible for as a result of their participation in the research, including but not limited to: clinical services required by the protocol deemed billable to insurance, transportation to study visits, parking, costs of drugs,

cost of therapy, lost broken or stolen devices, etc. Participants will be responsible for covering any costs associated with transportation to assessment meetings and classes. All venues associated with the study will have free, accessible parking.

2. Explain who will be responsible for payment of provided services in the event of insurance denials. Not applicable.
3. List what procedures, drugs, devices, supplies will be paid by the study sponsor or covered by other funding. List the other funding source. Supplies necessary to participate in the classes will be covered by the study sponsor. This includes groceries and supplies required for cooking activities.

## 26.0 Research Participant Compensation

There is no compensation or reimbursement for research participants – *please leave rest of this section blank*

There is compensation for research participants.  
**Describe the schedule, payment method, and payment total of any incentives or compensation that research participants will receive for participation in the research (e.g., gift cards or cash with amount, t-shirts, devices, bags, swag, etc.)** Participants will be compensated for the completion of the baseline/first and second assessments and compensated for each completed post-class survey. Participants will receive \$125 (cash) for completing the survey, food waste tracking, and 24 hour diet recalls before the classes begin and an additional \$125 (cash) for completing the survey, food waste tracking, and 24 hour diet recalls after the cooking classes end. Participants will be encouraged to eat the food prepared during classes and will receive a grocery bundle (~\$15 value) and cooking gadget (\$15 value) at the end of each class attended. Participants will receive \$5 (cash) for completing a feedback survey on each lesson attended, for a maximum of \$40 (cash) total for feedback surveys. Participants who complete at-home cooking challenges and post photos as proof to the class group chat, will be entered into a drawing to receive a pressure cooker. Each completed cooking challenge, as evidenced by submitted photo, will result in one submission for the drawing. For the focus group sessions, participants will receive a \$25 electronic gift card for participating in each of the 2 focus groups.

There will be reimbursement for research participants.  
**Describe the schedule, payment method, and payment total of any reimbursement that research participants will receive for participation in the research (e.g., gift cards or cash with amount, etc.)** Click here to enter text.

## 27.0 Compensation for Research Related Injury

Describe who will pay for the costs of medical treatment and/or compensation in the event of a research related injury:

Funding agency is providing some/all payment for injury

Funding agency is providing no payment for injury

N/A

## 28.0 Provisions to Monitor the Data to Ensure the Safety of Research Participants

1. Describe how often the data will be monitored for completeness, accuracy and adherence to the protocol. During the course of the 8-week Nourish curriculum, data will be monitored for completeness, accuracy, and protocol adherence daily as participants will be submitting post-class surveys during the time periods between consecutive classes, with special attention to the times immediately before and after classes when participants are likely to be submitting online surveys.
2. Indicate if there will be a Data and Safety Monitoring Board or Committee:  
 There will not be a formal Data and Safety Monitoring Board/Committee.

There will be a formal Data and Safety Monitoring Board/Committee.

Provide information about the DSMB/C including the contact information of the committee member(s) (as applicable); whether it is independent from the study sponsor; how often it meets; the type of data that will be used; written reports, etc. Click here to enter text.

## 29.0 Additional Information

*If you have any additional information regarding your study not covered in the template, please include it here.* Click here to enter text.

## 30.0 Devices

Does the study include the use of a device that is integral to the study question?

Yes – Answer the questions below.  
 No – Leave the rest of this section blank.

There is an active IDE (Investigational Device Exemption) for the proposed study.  
*Attach an official letter of support or proof of approval which identifies the IDE holder and IDE number to the SpartaIRB smartform.*

List devices: Click here to enter text.

The device has obtained a 501k clearance.  
*Attach 501k documentation to the SpartaIRB smartform.*  
List devices: Click here to enter text.

The device meets the criteria for an IDE Exemption.  
*Download the IDE Exemption Form from the SpartaIRB library (HRP-580) and attach to the SpartaIRB smartform.*

List devices: Click here to enter text.

The device (and its use) is a non-significant risk device for the proposed study design.  
List devices here and provide the PI's rationale for the non-significant risk device determination. [Click here to enter text.](#)

If the research involves device(s), describe your plans to use, store, handle, administer and track those device(s) to ensure that they will be used only on research participants and be used only by authorized investigators. [Click here to enter text.](#)

### 31.0 Community-Based Participatory Research

This is not a community-based participatory research project – [please leave the rest of this section blank](#)

This is a community-based participatory research project  
[Describe the involvement of the community in the design and conduct of the research.](#)  
[Click here to enter text.](#)

Note: Community based research is research that is conducted as an equal partnership between academic investigators and members of a community. In Community Based Participatory Research (CBPR) projects, the community participates fully in all aspects of the research process.

